#### **7.3.2. Replacement policy**

No patient who has been randomized and withdraws from the study for any reason will be replaced.

## 8. ADVERSE EVENTS

### 8.1. DEFINITIONS

#### 8.1.1. Definition of an Adverse Event

An adverse event (AE) is defined as any untoward medical occurrence in a patient or clinical investigation subject administered a medicinal product and which does not necessarily have a causal relationship with this treatment. An AE can therefore be any unfavorable and unintended sign (including an abnormal laboratory finding), symptom, or disease temporally associated with the use of a medicinal product, whether or not related to the medicinal product [*Clinical safety data management: Definitions and Standards for Expedited Reporting*].

#### 8.1.2. Definition of a Serious Adverse Event

A Serious Adverse Event (SAE) is defined as any untoward medical occurrence that at any dose:

- results in death,
- is life-threatening (i.e. the patient was at risk of death at the time of the event. It does not refer to an event which hypothetically might have caused death if it were more severe),
- requires inpatient hospitalization or prolongation of existing hospitalization,
- results in persistent or significant disability/incapacity,
- is a congenital anomaly/birth defect,
- is an important medical event that based upon appropriate medical judgment, may jeopardize the patient and may require medical or surgical intervention to prevent one of the outcomes listed above.

All AEs should be followed-up to determine the outcome of the reaction. The Investigator should follow up the event until resolution or stabilization of the condition. It is the Investigator's responsibility to assure that the subjects experiencing an AE receive definite treatment for any AE, if required.

### 8.2. EMERGENCY PROCEDURES

The treatment allocation for each patient will be provided in individual tamper-resistant decoding systems (sealed envelopes or scratch cards) to the Dompé Pharmacovigilance department.

The Investigator can request treatment allocation for a patient to an independent facility (either by telephone or web based system) in case of emergency where knowledge of the double-blind treatment may influence the further care of the patient.

If a code is opened for any reason, the reason behind it will be recorded.

### 8.3. RECORDING

AE data should be obtained through observation of the patient, from any information volunteered by the patient, or through patient questioning. Specifically, patients will be asked about any episode of documented hypoglycemia and ketoacidosis-related events occurring from the transplant day up to day  $75 \pm 14$  post-transplant. Any episodes will be reported as an AE or SAE, as appropriate. In addition, the Investigator will capture and report episodes of non-documented hypoglycemia throughout study participation.

All AEs (serious and non-serious) encountered during the clinical study will be recorded in the appropriate section of the CRF as per the recording period defined in paragraph 8.3.1. It is important that this includes the duration of the AE (onset/resolution dates), the relationship to the drug, the severity, the outcome and relevant concomitant treatments dispensed (or other action taken) (see Sections 8.3.2. and 8.3.3. below).

### 8.3.1. AE recording period

All AEs (serious and non-serious) which occur during each hospital stay will be recorded in the CRF. In addition, SAEs and relevant untoward events that occur subsequent to each hospital discharge will be recorded in the CRF.

### 8.3.2. Relationship of AEs to the Investigational Product

The Investigator will assess the possible relationship between the AE and the investigational medication, according to the criteria in the **Table** below:

#### Relationship of the Adverse Event to the Investigational Product

None (Intercurrent Event)	An event that is not and cannot be related to the Investigational Product, e.g. a surgical intervention for nevus removal performed during the study, but planned before patient enrolment into the study
Unlikely (remote)	Relationship is not likely e.g. a clinical event including laboratory test abnormality with temporal relationship to drug administration which makes a causal relationship improbable and in which other drugs, chemicals or underlying disease provide more plausible explanations
Possible	Relationship may exist, but could have been produced by the patient's condition or treatment or other cause
Probable	Relationship is likely, the AE abates upon discontinuation of Investigational Product and cannot be due to the patient's condition
Highly Probable	Strong relationship, the event abates upon discontinuation of Investigational Product and, if applicable, re-appears upon repeat exposure

An **Adverse Drug Reaction (ADR)** is defined as an adverse experience which is a reasonably likely to have been caused by the drug. Any AE reported in the study having a possible, probable or highly probable relationship to study drug will be considered as an ADR.

### 8.3.3. Severity of AEs

The Investigator will grade the severity of any AE using the definitions in the **Table** below. For each episode, the highest severity grade attained should be reported.

**Severity of the Adverse Event**

Mild	Grade 1 - Does not interfere with patient's usual function (awareness of symptoms or signs, but easily tolerated [acceptable]).
Moderate	Grade 2 - Interferes to some extent with patient's usual function (enough discomfort to interfere with usual activity [disturbing]).
Severe	Grade 3 - Interferes significantly with patient's usual function (incapacity to work or to do usual activities [unacceptable])

**8.4. SERIOUS ADVERSE EVENT REPORTING****8.4.1. Reporting Procedure for Investigators to Dompé (or designee)**

The Investigator must report all SAEs, regardless of presumed causal relationship, to Dompé (or designee) by fax or e-mail within 24 hours of learning of the event. Contact details for SAE reporting are provided in the section "Contact Information".

Information on SAEs will be recorded on a specific Non-Carbon Repeat SAE form. Both electronic and blank paper copies will be included in the Investigator's Site File. Follow-up reports (as many as required) should be completed and faxed/e-mailed following the same procedure above.

Whenever more than one SAE is observed, the Investigator should identify which is the primary adverse event, i.e. the most relevant one. If other events are listed in the same report, the Investigator, along with their relatedness to the Investigational Product, should identify which adverse events are serious and which are non-serious. In any case, the Investigator is requested to record his/her opinion about the relatedness of the observed event(s) with the investigational medication.

**8.4.2. Reporting Procedure for Investigators to IRB**

In addition to reporting the SAE to Dompé, the Investigator must also comply with the requirements related to the reporting of SAEs to the IRB which approved the study.

The requirements of IRB varies from one state and indeed one IRB to another; however, as a minimum requirement, the Investigators must promptly report all serious unexpected\* ADRs, life-threatening problems or deaths to their IRB.

Dompé (or designee) will inform Investigators of all serious unexpected ADRs which are reported to Dompé from other Investigators. These SAEs should also be reported promptly to the IRB in compliance with the local regulations.

Copies of all correspondence relating to reporting of any SAEs to the IRB should be maintained in the Investigator's Files.

\* For the purpose of this study, all ADRs are assumed to be unexpected.

**8.4.3. Reporting Procedures to the FDA**

During the course of the clinical trial, Dompé (or designee) shall inform the FDA of any serious unexpected ADR\* as soon as possible and in no event later than:

(a) seven calendar days after becoming aware of the information if the event is fatal or life threatening; and

(b) fifteen calendar days after becoming aware of the information if the event is neither fatal nor life threatening.

Dompé (or designee) shall, within 8 days after having informed the FDA under paragraph (a), submit a complete report in respect of that information that includes an assessment of the importance and implication of any findings made.

Furthermore, Dompé (or designee) shall follow up safety information and shall report final findings in a written safety report as soon as the relevant information is available.

If the results of an investigation show that an adverse drug reaction not initially determined to be reportable is reclassified as reportable, Dompé (or designee) shall report such reaction in a written safety report as soon as possible, but in no event later than 7/15 calendar days after the determination is made.

Dompé (or designee) will inform the FDA of all serious ADRs which are reported from other Investigators.

#### **8.5. ADVERSE EVENT EXEMPTION**

The following events will neither require recording nor reporting, as they are considered routinely associated to the pancreatectomy or to the transplant procedures:

- Delayed Gastric Emptying requiring insertion of a central line for Total Parenteral Nutrition or insertion of a nasojejunal tube for Enteral Nutrition;
- Increased ALT/AST levels up to 5 x ULN, inclusive, within 2 weeks post transplant;
- Abnormal PTT and INR values during prophylactic anticoagulation.

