### **6.5.1. Other treatments**

Drugs required during surgery will be administered as per centre practice.

The following prophylactic anticoagulation is suggested to be used in patients enrolled in this study

- Heparin will be administered at a dose of 70 U/kg, divided equally between the islet bags, followed by 3 U/kg/hour infused i.v. for the next 4 hours. From the 5th to the 48th hour post-transplant, heparin will be titrated to achieve and maintain PTT in the range 50-60 seconds. Comparable marker other than PTT will be used as per site experience.
- Enoxaparin will be administered at a dose of 30 mg subcutaneously from day 2 to 7 post-transplant.

Prophylactic anticoagulation management (choice of medication and/or doses) might be adjusted on the basis of clinical requirements (e.g. occurrence of bleeding) and/or centre practice. Low Molecular Weight Sulfate Dextran cannot be used in this trial.

Glycemic control in the early post-transplant period will be achieved by insulin administration to target glucose levels in the range 80-180mg/dL. Patients will be tested for blood sugar by fingerstick a minimum of 4 times per day. Insulin will be titrated to maintain fasting and pre-meal blood sugars in the range 80-125 mg/dL, and 2 hour post-prandial glucoses <180 mg/dL. For patients on continuous enteral or parenteral feeds, insulin will be titrated to maintain glucose in the range 80-140 mg/dL.

The following medications should not be used in this study:

- Systemic steroids (i.e. intravenous, intramuscular, oral; intra-articular injection allowed): from 2 weeks prior to enrolment up to the end of the study; use of  $\leq 5$ mg prednisone daily or equivalent dose of hydrocortisone, for physiological replacement only is allowed.
- Any investigational agents: from 4 weeks prior to enrolment up to the end of the study;
- Any anti-cytokine/chemokine medications (e.g. anti-TNF $\alpha$ ): from 4 weeks prior to enrolment up to the end of the study;
- Any immune modulators: from 4 weeks prior to enrolment up to the end of the study;
- Low Molecular Weight Sulfate Dextran;
- Oral hypoglycemic agents and any drugs that influence insulin sensitivity.

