#### **9.4.5. Interim analysis**

Safety and efficacy data will be reviewed on an ongoing basis by a DMC. Full details of the activities and responsibilities of the DMC are provided in the study DMC Charter.

Primary endpoint data will not be available until each patient reaches one year post randomization. Hence, it is expected that the majority of enrolment and treatment will be completed before meaningful evidence is available regarding treatment effect on the primary endpoint. Thus, traditional group sequential methods would have more limited utility in this setting.

The DMC will give careful consideration to the appropriateness of trial continuation if there is emerging evidence that Reparixin is harmful. One component of this assessment will be the rate of unexpected deaths. Based on historical experiences from the published Minnesota series for 1977-2011 that includes 356 adults, 217 underwent pancreatectomy and IAT from 2006-2011. There was 1 unexpected death within 12 months of transplant. This translates to an estimated 0.5% rate.

The DMC will consider the following guidelines regarding early termination based on the occurrence of unexpected deaths. Early termination will be considered if:

- there are at least 2 unexpected deaths in the first 33 reparixin patients (an outcome with 1.2% chance if the true event rate is 0.5%);
- there are at least 3 unexpected deaths in reparixin patients at any time in the trial (an outcome with 0.2% chance in 50 reparixin patients if the true event rate is 0.5%).

In making any recommendations about termination, the totality of data will be considered, including the number of unexpected deaths in the control group, and the available evidence about efficacy and the overall safety profile.

The DMC will also give particular attention to clinically significant coagulation abnormalities, including but not limited to intra-abdominal or gastrointestinal hemorrhage. Early termination would be considered if the rate of clinically significant post-surgical complications that require reoperation reliably exceeds the rate expected currently in standard practice settings. Insights about that rate in standard practice settings will be provided by a literature review, and will include the publication for the Minnesota series, where intra-abdominal as well as gastrointestinal hemorrhage have been reported to be the most common reasons for reoperation (*Sutherland, 2012*).

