## 14. APPENDICES

### 14.1. APPENDIX 1 – CUMULATIVE SUMMARY OF ADVERSE DRUG REACTIONS

MedDRA Body System / LLT	Non Serious	Serious	Frequency
Blood and lymphatic system disorders	3	1	4.30%
Anaemia	2		
Coagulopathy		1	
Lymphadenopathy	1		
Cardiac Disorders	1	0	1.08%
Tachycardia	1		
Gastrointestinal Disorders	13	0	13.98%
Abdominal pain NOS	1		
Dyspepsia	1		
Flatulence	2		
Gastroesophageal reflux disease	1		
Nausea	6		
Vomiting	2		
General disorders and administration site conditions	21	0	22.58%
Canula site reaction	13		
Fatigue	1		
Injection site thrombosis	3		
Infusion site oedema	2		
Lethargy	1		
Oedema peripheral	1		
Immune system disorders	0	1	1.08%
Lung transplant rejection		1	
Injury, poisoning and procedural complications	1	0	1.08%
Complications of transplanted kidney	1		
Investigations	2	0	2.15%
Blood amylase increased	1		
Liver function test abnormal	1		
Metabolic and nutrition disorders	1	0	1.08%
Hyperkalaemia	1		
Musculoskeletal and connective tissue disorders	1	0	1.08%
Arthralgia	1		
Nervous system disorders	25	0	26.88%
Dizziness	3		
Headache	8		
Hypoesthesia	3		
Somnolence	11		
Psychiatric disorders	4	0	4.30%

Adverse Drug Reactions - Number of Reports by Terms			Frequency
MedDRA Body System / LLT	Non Serious	Serious	
Abnormal dream	1		
Restlessness	1		
Euphoric mood	2		
Renal and urinary disorders	4	0	4.30%
Renal failure	1		
Renal tubular necrosis	2		
Urinary retention	1		
Respiratory, thoracic and mediastinal disorders	6	1	7.53%
Bradypnoea	1		
Cough	2		
Nasopharyngitis	2		
Respiratory failure		1	
Sore throat	1		
Skin and subcutaneous system disorders	4	0	4.30%
Erythema	1		
Infusion site erythema	2		
Pruritis	1		
Vascular disorders	1	3	4.30%
Haemorrhage		1	
Hypotension	1		
Retroperitoneal haemorrhage		2	
TOTAL	87	6	

1 = table does not include ADRs reported from the ongoing pilot trial in islet allo-transplant patients

The most frequent (>10%) ADRs observed in the phase 1 and phase 2 studies were:

Nervous system disorders (about 27%), including headache, dizziness, hypoaesthesia, somnolence.

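### Protocol 8.5 waives recording and reporting of its listed events even when they are serious, against 8.4.1; delayed gastric emptying needing TPN or a tube then drops out of every by-arm table

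*Protocol*

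**What the plan says.** Protocol 8.1.1 counts an abnormal laboratory finding as a possible AE. Section 8.3.1 asks for all AEs during the hospital stay, and for SAEs and relevant untoward events afterwards. Section 8.1.2 makes hospitalization, or a longer stay, a seriousness criterion. On serious events 8.4.1 is categorical: "The Investigator must report all SAEs, regardless of presumed causal relationship", with a 24-hour limit.

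Section 8.5 then introduces three items with "The following events will neither require recording nor reporting, as they are considered routinely associated to the pancreatectomy or to the transplant procedures":

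- The first item has no limit of duration: "Delayed Gastric Emptying requiring insertion of a central line for Total Parenteral Nutrition or insertion of a nasojejunal tube for Enteral Nutrition".
- The second is capped in size and in time: "Increased ALT/AST levels up to 5 x ULN, inclusive, within 2 weeks post transplant".
- The third is bounded only by the period of anticoagulation: "Abnormal PTT and INR values during prophylactic anticoagulation".

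None of them sets aside events that are serious or clinically significant.

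Two other places bear on this. Protocol 6.5 lists parenteral nutrition and enteral feeds among the agents that need not be recorded as concomitant medication. Protocol 9.4.5 states: "The DMC will also give particular attention to clinically significant coagulation abnormalities". Section 12.5 repeats that duty and names SAEs as the main safety data for the DMC.

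**The concern.** A site faced with a listed event that prolongs the stay is told by 8.4.1 to report it and by 8.5 that it need not. Different sites may resolve this differently.

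The reason given for the exemption is that the events are routine after this surgery. In a placebo-controlled trial that is not a reason to leave them out. The placebo arm shows the background rate, and an excess on drug is visible only if events are recorded in both arms. At stake are the completeness of the SAE tables, what reaches the DMC, and the expedited route to the FDA. Sections 8.4.2 and 8.4.3 treat all ADRs as unexpected and set limits of 7 or 15 days, so a serious listed event thought possibly drug-related would leave that route too.

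**Working it through.** No sample-size or error-rate calculation applies. The check is to follow each exempt event through every route by which a difference between arms could be seen.

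**Step 1: does the waiver reach serious events?** Section 8 sets out a reporting procedure only for SAEs (8.4); other AEs are recorded under 8.3. A waiver of reporting as well as recording therefore most naturally includes SAEs, and nothing in 8.5 says otherwise. The conflict with 8.4.1 is in the text.

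**Step 2: what other routes remain?**

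| Route | Delayed gastric emptying with TPN line or nasojejunal tube | PTT/INR abnormality during prophylaxis |
|---|---|---|
| AE and SAE tables (SAP 7.6.1) | Entry not required | Entry not required |
| Safety endpoint (Protocol 4.2.3) | None | INR/PTT daily on Days 1-7, and at discharge |
| By-arm laboratory summary | None | Descriptive summaries and box plots (SAP 7.6.2.2); investigator's clinical-significance flag at discharge (SAP 7.6.2.1) |
| Concomitant medication (SAP 7.4.6) | Feeds exempt (Protocol 6.5) | Does not carry the values |

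Weight, albumin, pre-albumin and malnutrition risk at Days 75 and 365 may be affected by poor gastric emptying but do not identify it. SAP section 10 plans listings of hospital discharge and post-transplant glycemic control. Their content is not described, and no by-arm table is built on them.

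**Step 3: which gastric-emptying cases are lost?** Let *m* be the cases not needing a line or tube and *s* those that do. Section 8.3.1 still asks for *m* during the hospital stay, while 8.5 exempts *s*. The required count is *m* = (*m* + *s*) − *s*. If treatment moved patients from *m* to *s*, the recorded count in that arm would fall. The cases needing intervention are the ones left out.

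**Step 4: what is lost for PTT/INR?** Only the rating of severity, relatedness and seriousness. The daily summaries carry no clinical-significance flag between screening and discharge, and clinically significant abnormality is the category named for the DMC. Under the suggested regimen, enoxaparin is given "subcutaneously from day 2 to 7 post-transplant", so the daily values cover most of the exempt period. If a centre continues longer, as 6.5.1 allows, only the discharge test remains.

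**The case against.** The strongest reply is that little is lost. INR, PTT and ALT/AST are listed safety endpoints, collected daily and summarized by arm, and ALT/AST also gets a by-arm repeated-measures model. Bleeding and reoperation are not in 8.5 and appear in the preferred-term tables. The DMC sees unblinded data, with the SAP as guide to its outputs. The wording lifts a requirement and does not forbid recording. Patients may go home on enteral or parenteral nutrition (7.1.5), so delayed gastric emptying need not prolong the stay.

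All of this stands, and it confines the coagulation part to classification. It does not answer the conflict with 8.4.1 or the gastric-emptying gap. Optional recording leaves that count to each site's habit.

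Some stronger readings are tempting but not supported:

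- **PTT/INR is exempt without limit, or the DMC is blind to coagulation.** The exemption is tied to prophylactic anticoagulation, the values are still collected, and a bleed or a diagnosed coagulopathy remains reportable.
- **Appendix 1 shows that most serious reactions are bleeds.** The six serious reports are two of "Retroperitoneal haemorrhage", one haemorrhage, one coagulopathy and two others. Haemorrhage is 3/6 = 50%; only with coagulopathy is it 4/6 = 67%. Section 8.5 does not exempt haemorrhage, so neither fraction measures what is removed.
- **The exemption hides the drug's known gastrointestinal reactions.** These are 13 of 87 + 6 = 93 reports (13.98%, as printed): nausea 6, vomiting 2, flatulence 2, and abdominal pain, dyspepsia and reflux 1 each. None is delayed gastric emptying and none was serious.
- **The ALT/AST item conflicts with the hepatic discontinuation rule.** That rule in 6.3.2 also needs raised bilirubin, which is not exempt, and the reason for discontinuation must be recorded.

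**Conclusion.** The point holds in a limited form. Section 8.5 contradicts 8.4.1 for any listed event that is serious. For delayed gastric emptying needing a TPN line or nasojejunal tube, the comparison between arms is lost: exempt events left unrecorded add 0 to every AE, SAE and medication table, whatever the true rate in either arm. For PTT/INR the loss is AE/SAE classification during prophylaxis, not the data.

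The number of events affected cannot be estimated, because the documents give no background rate for delayed gastric emptying. The conclusion assumes that sites use the exemption as written and that the CRF, which is not among the documents, has no separate field for the event. A field that was only listed would soften the gap but would still give no planned comparison. The documents do not show that the drug causes delayed gastric emptying or that a bleeding signal would be missed.

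**What to change.** Reconcile 8.5 with 8.4.1:

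1. State that no exemption applies to an event meeting any criterion in 8.1.2.
2. State that none applies to a PTT/INR abnormality that the investigator judges clinically significant, the category in 9.4.5 and 12.5. No numerical threshold is needed.
3. Record delayed gastric emptying, with or without a line or tube, on the AE page. The existing by-arm tables in SAP 7.6.1 will then count it.

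The cost is protocol wording and a few more AE lines per patient, with a higher count of procedure-related AEs in both arms. The benefit is limited by timing. The amendment's rationale gives 86 patients transplanted against a goal of 100, so prospective capture would reach about 100 − 86 = 14 more transplanted patients from that date. For those already treated, sites could be asked, before database lock and unblinding, whether any serious event was left unreported under 8.5. The study report should say which patients were followed under which rule.
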